## **Statistical Analyses**

Prior to data analyses, the data collected under this study will be combined with data from its VA counterpart (IRB #2014-0939). Statistical analyses will be performed using this combined data set.

**Aim 1:** A repeated measures analysis model will be used to model changes in tongue strength in treatment and control groups, adjusted for age, gender, and baseline tongue strength. Each subject will have three observations: change between baseline and 8 weeks, baseline and 12

weeks, and 8 weeks and 12 weeks. This model will allow for comparison of differences between a) treatment durations (dose response) and b) between control and treatment groups.

**Aim 2:** Changes in oral intake and swallowing quality of life between baseline and 8 weeks, baseline and 12 weeks, and 8 weeks and 12 weeks will be modelled in a repeated measures analysis on treatment, adjusting for age, gender, and baseline outcome.

**Aim 3:** Change in number of new pneumonia diagnoses and number of hospital readmissions over a 1 year period, pre and post-study, will be modelled in linear regression models on treatment, adjusting for age, gender, and pre-study outcome.

All analyses will be performed on a randomized, or intention to treat basis, regardless of the actual treatment received. Study dropout by the subject will result in inclusion of incomplete data for that patient.

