## **Research Design and Methods:**

### **Subjects**

Forty medically stable unilateral ischemic stroke subjects with dysphagia will be consecutively accrued from the University of Wisconsin Hospital and Clinics (UWHC). There is a counterpart application that is currently under review with the IRB for enrollment of Veterans into this study as well (IRB #2014-0939). Therefore, the forty subjects will be the sum of those enrolled through this protocol as well as the VA protocol under review.

Recruitment Process: Inpatients or Outpatients who meet the inclusion criteria related to their stroke diagnosis (unilateral or bilateral ischemic or hemorrhagic stroke within 6 months of diagnosis) with none of the exclusion criteria will be referred by [name], a stroke neurologist and Medical Director of the UW Comprehensive Stroke Program or a member of his team, to participate in the study. Patients also may be referred by the UW Voice and Swallowing Clinic clinicians involved in this study. In order to have earlier identification of inpatients who are potential participants, [name], an Emergency Department physician, will be screening the list of admitted emergency patients daily for those who meet study criteria based on stroke diagnosis. He will then notify [name] of these potential participants and she will confirm eligibility with [name], his team, or the ENT clinicians. Once general eligibility for meeting inclusion criteria is confirmed via [name] review of the patient's medical record and it has been determined that the patient will require videofluoroscopic examination (VFSE) of his/her swallowing as part of routine clinical care, [name], a member of his team, or a clinician from the UW Voice and Swallowing Clinic will ask the patient to fill out a permission-to-contact form and subsequently will notify [name] that this form has been signed so that she can follow-up with the patient.

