## **Intervention**

Participants who meet criteria for dysphagia on the videofluoroscopic swallowing examination will be randomly assigned into one of two groups: 1) a control group that will be receiving compensatory treatments only or 2) 12-week DF I-PRO therapy *plus* compensatory treatments, such as thickened liquids and/or postural strategies during natural swallowing activities for 12 weeks. Patients will be enrolled and trained in DF I-PRO therapy by [name] who regularly uses the SwallowSTRONG®-facilitated I-PRO therapy in clinical practice or a UW Voice and Swallowing clinician involved in this study who has been adequately trained in DF I-PRO therapy. Regardless of the treatment group to which a subject is randomized, they will be evaluated in the hospital at baseline and 8-week time points. If a patient in either group no longer meets criteria for dysphagia (Penetration-Aspiration Scale score of 3 or higher OR a rating of 2 on the Residue scale in any location) on the 8-week videofluoroscopic swallowing examination, s/he will no longer continue participation in the study. If a patient in either group remains dysphagic at the 8-week visit, s/he will continue participation in the study through the 12-week assessment point. [name] or a UW Voice and Swallowing clinician will conduct the 8 and 12 week assessments.

**Group 1: Compensatory treatments only:** This group will receive standard swallowing intervention, which is identified by the SLP as appropriate to treat the patient's dysphagia and is common clinical practice. This group is not receiving experimental therapy. Their therapy may include: 1) modifying the foods the subject eats or the fluids s/he drinks; 2) changing his/her posture when eating or drinking (for example, by a simple chin tuck) or using a swallowing maneuver while eating or drinking; 3) having him/her eat more slowly or in a quiet environment to make swallowing easier and safer; or 4) performing range of motion or vocal exercises for

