## **Outcomes**

The *primary outcome measure* will be changes in the *one repetition maximum (IRM) isometric lingual pressures* measured at the front and back sensors of the device. Secondary outcomes include *bolus flow durational measurements* taken from videofluoroscopic recordings, *swallowing pressures, SWAL-QOL scores, and FOIS scores*. In addition, we will compare the *number of pneumonia diagnoses* for community, hospital-acquired, and aspiration pneumonia for the same period of time prior to enrollment and following completion of the study (up to nine months). We also will track the *number of hospital re-admissions* for the same period of time prior to enrollment and following completion (up to 9 months). Treatment compliance also will be tracked within the SwallowStrong® device and will serve as a covariate in statistical analyses.

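### Data from two protocols, University and VA, are pooled, but no Aim 1-3 model has a site term and no stratification by site is stated

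*Combined protocol and SAP*

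**What the plan says.** The Subjects section explains that enrolment runs through this protocol and a VA counterpart with its own IRB application, and that "the forty subjects will be the sum of those enrolled through this protocol as well as the VA protocol under review". The split between the two is not given. The Statistical Analyses section says that, before analysis, "the data collected under this study will be combined with data from its VA counterpart", and adds: "Statistical analyses will be performed using this combined data set".

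On allocation, the Intervention section says only that participants who meet the dysphagia criteria "will be randomly assigned into one of two groups". It states no ratio, blocking or stratification, and does not say whether one list serves both protocols. The VA protocol's own method is not described in these documents.

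The covariates are:
- Aim 1: "adjusted for age, gender, and baseline tongue strength"
- Aim 2: "adjusting for age, gender, and baseline outcome"
- Aim 3: "adjusting for age, gender, and pre-study outcome"

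The Outcomes section adds treatment compliance, which "will serve as a covariate in statistical analyses". Site or protocol appears nowhere as a covariate, stratum or random effect.

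**The concern.** Two cohorts run under separate protocols are analysed as one, and nothing in the stated design or models accounts for which cohort a subject came from. A site difference in mean change is plausible from the text. The control condition is standard care chosen by the treating clinician from several options, so it can vary by institution. The Aim 3 counts come from discharge reports and clinic notes, and the record systems named are the University's.

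What is at stake depends on how subjects are allocated:
- **Separate lists by protocol, same ratio.** The design balances site, but the analysis ignores that. Between-site variation stays in the residual, the standard error is too wide and the test is conservative.
- **One common list.** The arms can differ in VA share by chance, and the model does not adjust for it.
- **Different ratios in the two protocols.** Site is then confounded with treatment, and the group difference is biased whenever sites differ.

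In all three cases the residual SD carries between-site variation. This matters because the Project Summary and Specific Aims say that the results will be used to size a larger trial.

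**Working it through.** **Inputs from the plan (Sample size calculation).** 15 per group, SD of change 100 hPa, alpha 0.05, expected changes of 100 and 20 hPa (difference 80 hPa), stated power 56%.

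**Assumed, because the documents are silent.** VA share of the 30 subjects and site difference *g* in mean change (0 to 100 hPa).

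**1. The plan's own figure.** SE of the difference = 100 × √(2/15) = 36.5 hPa. Two-sided t-test power on 28 df (noncentral t) is 75.3%, 56.2%, 35.5% and 18.5% for 100, 80, 60 and 40 hPa. Table 2 gives 75%, 56%, 35% and 18%, so it reproduces.

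**2. Chance imbalance under one common unstratified list.** With *m* VA subjects among 30, the number in one arm of 15 is hypergeometric.

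| VA subjects | Chance that VA share differs by ≥20 points | SD of difference in share | Typical shift, g = 50 | Typical shift, g = 100 |
|---|---|---|---|---|
| 6 | 17% | 0.15 | 7 hPa | 15 hPa |
| 9 | 43% | 0.17 | 9 hPa | 17 hPa |
| 15 | 47% | 0.19 | 9 hPa | 19 hPa |

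Typical shift = *g* × SD of the difference in share (unrounded), to be read against the SE of 36.5 hPa. In simulation with common 1:1 allocation, the average bias is nil and type I error is near 5% without a site term.

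**3. Bias if ratios differ.** Bias = *g* × (VA share in treatment − VA share in control). As an illustration, take 8:12 at the University and 7:3 at the VA: (7/15 − 3/15) × 50 = 13.3 hPa. This bias is systematic and does not average out.

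**4. Power with the planned covariates.** Simulation of a linear model for one change score per subject, with 5,000 runs. Assumptions: 30 subjects, 12 of them VA; 95% of VA and 50% of University subjects male; within-site SD 100; true effect 80 hPa; age, gender and baseline in the model with no effect of their own.

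| Allocation | Site difference | Power without site | Power with site |
|---|---|---|---|
| Unstratified | 0 | 51.9% | 49.9% |
| Unstratified | 25 | 51.5% | 50.1% |
| Unstratified | 50 | 50.0% | 49.9% |
| Unstratified | 100 | 45.5% | 51.0% |
| Stratified | 0 | 50.4% | 49.7% |
| Stratified | 50 | 48.7% | 50.0% |
| Stratified | 100 | 42.9% | 49.7% |

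Under stratified allocation with *g* = 100 and no site term, type I error is about 3%; a site term restores it to about 5%. Under unstratified allocation, keeping both gender and site raises the mean treatment SE from 38.2 to 39.0 hPa (39.0/38.2 = 1.02, about 2%).

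**5. Residual SD carried into the next trial.** With no covariates and 40% VA, the SD is √(100² + 0.4 × 0.6 × *g*²), which is 103 at *g* = 50 and 111 at *g* = 100. With the planned covariates, gender absorbs part of this and the SD is 101-102 and 108-111. Required n scales with SD². For 80% power at 80 hPa with SD 100, the normal approximation gives 2 × (1.96 + 0.84)² × 100²/80² ≈ 24.5 per group. Multiplying by 1.01² to 1.02² gives 25.0-25.5 (2-4% more). Multiplying by 1.08² to 1.11² gives about 28.6-30.2 (17-23% more).

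The repeated measures structure and the compliance covariate were not simulated, so the figures in steps 4 and 5 are indicative.

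**The case against.** The strongest reply is that the harm is conditional and may be nil. The documents give no site difference and no VA share. A clear gain in power needs a difference of about 100 hPa, which is one full SD and equals the whole improvement expected with therapy. Gender may already carry part of the site effect. Under unstratified allocation the term costs about 2 points at no difference and only breaks even near 50 hPa. Standard errors under randomisation already allow for chance imbalance, and a conservative test creates no false-positive risk. For Aim 3, one tallying method is described, and a constant site difference in recording would largely cancel in pre-post change. The VA protocol may also already randomise within site. All of this limits the size of the point, and most of it stands.

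Two things survive. Whether the protocols share a ratio or a list is not stated, so the one route to real bias is not closed. And the inflated residual SD feeds directly into the pilot's stated purpose, even though the test itself remains valid.

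Three stronger readings are tempting but not supported:
- **That omitting site biases the treatment effect or inflates type I error.** Under common equal-ratio allocation it does neither.
- **That precision is certainly wasted.** This depends on a site difference that the documents do not give.
- **That allocation is faulty or its ratios do differ.** The VA method is not visible here.

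**Conclusion.** The point holds as a cheap improvement to the analysis; the omission does not invalidate it. The plan pools two protocols, states no stratification by site and adjusts for site in no model. The consequence turns on two unknowns, how each protocol allocates and whether mean change differs by site. The loss is negligible if sites are alike. It becomes material as the difference approaches 100 hPa, where it reaches about 6 points of power and a 17-23% overstatement of the next trial's sample size. If ratios differ between protocols, the estimate itself is biased in proportion to the site difference. No figure can be given for Aim 3 from these documents.

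**What to change.** Add a fixed University/VA term to the Aim 1, 2 and 3 models. State for each protocol the allocation ratio, the list used and any stratification and, where still possible, randomise within each protocol at the same ratio. If site is left out, give the reason. Report the residual SD from the site-adjusted model as the input to the later sample size.

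The cost is one model term, one degree of freedom and a few sentences. If sites do not differ, power falls by up to about 2 points under unstratified allocation and by about half a point under stratified allocation. Gender can stay in the model beside site. The roughly 2% rise in the treatment SE, if VA subjects are nearly all male, is small but not zero.

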## **Specific Aims**

This randomized controlled pilot study will characterize effects of SwallowSTRONG® Device-Facilitated Isometric Progressive Resistance Oropharyngeal (DF I-PRO) therapy in a dose response framework on swallowing-related outcomes in a group of unilateral ischemic stroke patients. These results will be used to determine adequate sample size in order to support a larger clinical trial focused on the efficacy of this therapy approach for improving swallowing safety. This randomized study will expand upon previous work examining effects of this therapy approach on swallowing and health-related outcomes now limited to a heterogenous cohort of Veterans with dysphagia from a variety of etiologies. It will focus specifically on patients post-stroke who have been shown to experience improvements in swallow function following DF I-PRO therapy.

**Specific Aim 1:** To determine differences in swallowing physiology and bolus flow measures a) between a group of unilateral ischemic stroke subjects undergoing SwallowSTRONG® DF I-PRO therapy and controls and b) between 8 and 12 weeks of treatment.

**Hypothesis 1a:** Subjects treated with DF I-PRO therapy at both treatment duration points will demonstrate greater improvements in swallow physiology (isometric and swallowing pressures) as well as bolus flow measures (levels of airway invasion, post-swallow residue/stasis, oral transit times, and stage transition duration times) as compared to the control group.

**Hypothesis 1b:** Subjects treated with DF I-PRO therapy will experience improvements in swallow physiology and bolus flow measures at the 12 week duration compared to 8 weeks.

**Specific Aim 2:** To examine changes in level of oral intake and swallowing quality of life in post-stroke patients undergoing DF I-PRO therapy as compared to a control group and as they relate to treatment duration response at 8 weeks and 12 weeks

**Hypothesis 2a:** Patients undergoing DF I-PRO therapy will require less restrictive diets and will report improved swallowing-related quality of life compared to those in the control group at both treatment duration points.

**Hypothesis 2b:** Twelve weeks of DF I-PRO therapy will result in greater improvements (least restrictive diets and improved quality of life) compared to the 8 week duration.

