**Figure 1**

## **Visits**

**Baseline visit only:**

After the informed consent process has been completed but prior to videofluoroscopic examination of swallowing, each participant will complete a medical history questionnaire to ensure they meet inclusion/exclusion criteria. This questionnaire will include items related to current medical status, medical history, and medication usage. UW medical records also will be referenced to ensure the subject's eligibility for participation. As part of this screening, patients will undergo a urine pregnancy test to ensure they are not pregnant prior to participation. The Mini-Mental Status Examination (MMSE) will be administered only at baseline as a common examination of cognitive functioning. In addition, the Barthel index will be administered to assess severity of impairments in activities of daily living. For each patient, a form with demographics as well as a medication list will be filled out. These questionnaires and tests will take approximately 45 minutes to complete. For those subjects randomly assigned to Group 2, during this baseline visit, it also will take approximately 30 minutes to train the participant on how to do and record the exercises properly. In addition to the consent process and these procedures that will occur only at the baseline visit, the procedures described below will also be completed at this visit. The entire baseline visit will last about 2.5 hours. For the baseline visit and 8 week visit, videofluoroscopic examination of swallowing will need to be completed before the other procedures outline below as the outcome of that examination will determine the patient's continued participation in the study. If s/he does not meet criteria for dysphagia on the videofluoroscopic swallowing exam, s/he will either not be randomized to a study group (at baseline visit) or will not continue participation past the 8 week point (if dysphagia has resolved).

*Measures at each assessment point (baseline, 8 weeks, and 12 weeks):* The 8 week and 12 week visits will last about 90 minutes per session. The study includes up to 3 sessions which will require up to 7 hours in total. In addition if in Group 2, participation in the home exercises will last about 10 minutes per session, 9 sessions per week for up to 12 weeks, which will require up to 18 hours total.

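### The Aim 1 and Aim 2 models use three change scores from three visits; the third is redundant, so the covariance is singular and the 8-versus-12-week question gets two answers

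*Combined protocol and SAP*

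**What the plan says.** Statistical Analyses, Aim 1, specifies one repeated measures model of tongue strength, "adjusted for age, gender, and baseline tongue strength". Its response is set out as follows: "Each subject will have three observations: change between baseline and 8 weeks, baseline and 12" weeks, and then the change from 8 to 12 weeks. The paragraph adds: "This model will allow for comparison of differences between a) treatment durations (dose response) and b) between control and treatment groups".

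Aim 2 puts the same three scores into a repeated measures analysis: "Changes in oral intake and swallowing quality of life between baseline and 8 weeks, baseline and 12 weeks, and 8 weeks and 12 weeks".

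The Visits section gives three assessment points ("Measures at each assessment point (baseline, 8 weeks, and 12 weeks"). Hypothesis 1b in Specific Aims is that treated subjects "will experience improvements in swallow physiology and bolus flow measures at the 12 week duration compared to 8 weeks".

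Two further provisions matter. Under Intervention, a subject in either group who no longer meets the dysphagia criteria leaves at week 8: "on the 8-week videofluoroscopic swallowing examination, s/he will no longer continue participation in the study". Statistical Analyses keeps partial records: "Study dropout by the subject will result in inclusion of incomplete data for that patient".

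Neither aim names a covariance structure, a robust variance, or which quantity answers the 12-versus-8-week question.

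**The concern.** Three visits yield two independent changes. The third adds no information, yet the model treats it as another observation.

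- **Standard errors.** An unstructured covariance cannot be estimated. Compound symmetry, AR(1) and independence can be fitted but are misspecified, so model-based standard errors will generally be wrong.
- **Two answers.** The 12-versus-8-week effect can be read as the effect on the third score, or as the week-12 effect minus the week-8 effect. The two have different standard errors, and their estimates can differ.

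This is the model for the primary outcome, and the stated route to both the group and the dose-response comparisons.

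**Working it through.** **Inputs.** From Sample size calculation: 15 per group, SD of change 100 hPa in both groups, alpha 0.05. Not in the documents, so assumed: SD 100 hPa for the 12-week change as well, and the correlation r between the two changes from baseline.

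**1. The plan's own figure.** For a two-sided two-sample t-test on 28 df, the SE is 100 x sqrt(2/15) = 36.5 hPa. Differences of 100, 80, 60 and 40 hPa give power of 75.3%, 56.2%, 35.5% and 18.5%, which matches Table 2. The calculation uses a single change score, so this concern does not touch it.

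**2. Dependence.** Let D1 = Y8 - Y0, D2 = Y12 - Y0 and D3 = Y12 - Y8. Then D3 = D2 - D1 for every subject with both follow-ups. At r = 0.8 the variances are 10000, 10000 and 20000(1 - 0.8) = 4000. The covariances are 8000 (D1,D2), -2000 (D1,D3) and 2000 (D2,D3). The eigenvalues are 0, 6000 and 18000, so the rank is 2. The zero eigenvalue appears at every r. In one simulated data set the unstructured log-likelihood rose from -355 to -97 as the variance in the null direction fell from 100 to 0.000001; it has no maximum.

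**3. Compound symmetry, complete data, no covariates.** The fitted variance is the average v = 10000(4 - 2r)/3, and the fitted covariance is c = 10000r/3. The model SE of the arm difference is sqrt(2v/15) for each score and sqrt(2 x 2(v - c)/15) for the D2 - D1 contrast. The true SE is 36.5 at weeks 8 and 12, and sqrt(2 x 20000(1 - r)/15) for the 8-to-12 change. All are in hPa.

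| r | Model SE, any score | Model SE, contrast | True SE, 8-to-12 |
|---|---|---|---|
| 0.5 | 36.5 | 47.1 | 36.5 |
| 0.7 | 34.0 | 41.1 | 28.3 |
| 0.8 | 32.7 | 37.7 | 23.1 |
| 0.9 | 31.3 | 34.0 | 16.3 |

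Here the two 8-to-12 estimates are equal, but their SEs are not.

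**4. With the planned covariates on common slopes.** Each score's arm effect is its raw difference minus the same term, the sum of b_k x (arm difference in the mean of covariate k). That term cancels in D2 - D1 but stays in the D3 effect. The two estimates therefore differ by exactly that term, even with complete data.

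Simulated type I error (nominal 5%; 20,000 null replicates per setting; baseline-to-follow-up correlation 0.3 to 0.85; equal variance at all visits; ranges also cover 25, Satterthwaite or 56 df, except that the 0.65 row covers only Satterthwaite and 56):

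| r | Weeks 8 and 12 | Third score | Contrast |
|---|---|---|---|
| 0.5 | 2.7-4.9% | 5.0-9.3% | 1.0-1.5% |
| 0.65 | 4.1-6.1% | 3.4-7.0% | 0.7-0.9% |
| 0.8 | 5.0-7.7% | 0.9-3.7% | 0.2-0.3% |
| 0.9 | 6.4-9.1% | 0.2-1.6% | at most 0.05% |

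An independence structure at 0.8 gave 5.4-8.5%, 1.2-4.0% and under 0.1%.

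**5. Gap between the two answers, complete data.** The root-mean-square gap is 10-16 hPa between arms and 5-8 hPa within the treated arm. If baseline is unrelated to change, it is 8.8 and 4.4 hPa. The true between-arm SE at r = 0.8 is 23.1 hPa.

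**6. Week-8 exits (rates and mechanism assumed; r = 0.8, baseline correlation 0.5).** With exit tied to week-8 pressure, the between-arm gap grows from 14 hPa (no exits) to 31 (30%) and 42 (50%). Under a second assumed model, logistic in D1 with no true 8-to-12 difference, the third score averaged about +17 to +21 hPa and the contrast about -3 to -9 hPa.

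**7. Power for an assumed 40 hPa between-arm 8-to-12 difference, r = 0.8.** About 39% with the correct SE, 16-24% by the third score and 8% by the contrast.

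**8. Robust variance.** A subject-clustered sandwich SE gave type I error of 4.2-7.8% with complete data (r = 0.5, 0.8, 0.9) and 6.3-11.1% at 50% exits. It leaves the two answers in place.

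**The case against.** The strongest reply concedes the algebra and contests its weight.

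- **Hypothesis 1b concerns treated subjects, but the larger figures are between-arm.** This stands as a caution. The gaps of 10-16, 31 and 42 hPa and the power figures are not results for 1b as written. The treated-arm gap with complete data is 5-8 hPa. The conservative contrast does carry over to the treated arm (0.1-0.3% at r = 0.8).
- **The plan does not spell out common slopes or a treatment-by-score term.** True. If every covariate slope varied by score, the two estimates would coincide with complete data, but their SEs would still differ. Leaving out the treatment-by-score term does not help: D1 + D2 + D3 = 2 x D2, so one term averaged over the scores estimates two-thirds of the 12-week effect, for example 53 hPa when the effect is 80 hPa at both visits.
- **The 10-16 hPa range assumes equal variance at all visits.** It does, and the range extends down to 8.8 hPa when baseline does not predict change.
- **The effect on the week-8 and week-12 tests is small, and this is a pilot.** The first part is right: the distortion is modest and can go either way. But treatment duration is a stated aim, and that comparison is hit most consistently.
- **An unstructured fit would fail visibly, and a robust variance would help.** Both are true. Neither is in the plan, and neither decides which answer counts.

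**Conclusion.** The concern holds. The redundancy and the rank-2 covariance are exact and need no assumption. They apply equally to the Aim 2 outcomes, for which no size is claimed. No other section of the plan cures the problem.

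The sizes are illustrative. They rest on a chosen covariance structure, an assumed correlation and assumed exit rates, none of which the documents give. Within those limits, the 12-minus-8 contrast was conservative at every correlation tried (1.5% or less against 5%). The third-score test ran from 0.2% to 9.3%. The week-8 and week-12 tests ran from 2.7% to 9.1%, with the direction depending on the correlation. Table 2 is unaffected, and no effect on the size of the later trial is claimed. The plan should be corrected before analysis.

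**What to change.** In Aims 1 and 2, use two outcomes per subject: the week-8 and week-12 values, or the two changes from baseline. Fit treatment, visit, treatment-by-visit, baseline, age and gender with an unstructured 2x2 covariance and Kenward-Roger degrees of freedom. Keep subjects who have only week-8 data. Take the week-8 effect, the week-12 effect and their difference as contrasts from this one model, and state whether the 12-versus-8-week contrast is within the treated arm, between arms, or both.

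In the same simulation at r = 0.8, type I error for week 8 / week 12 / difference was 4.7/4.0/4.8% with no exits, 5.3/5.3/5.4% at 30% and 5.6/4.9/4.9% at 50%. At r = 0.5 and 0.9 it was 4.6-5.7% (no exits and 50% exits).

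Two matters remain for the authors. The plan must say how subjects who leave at week 8 enter the 12-versus-8-week contrast, because the model alone does not settle that. The check covered a continuous outcome only; FOIS is an ordered scale, and the suitability of a normal model for it was not tested.

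The cost is the wording of two paragraphs. It needs no new data, visits or patients, and dropping the third score loses no information.
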